#### Tests at above evaluation schedule:

- a. Renal function as assessed by the iothalamate clearance test starting at Baseline visit.
- b. Renal Function as assessed by serum creatinine, by Cockcroft-Gault formula mL/min, and 24 hour urine collection for creatinine clearance and urinary protein level starting at Baseline visit.
- c. Liver Recipient blood sample for genotype testing.
- d. Testosterone levels

The genetic tests will involve TaqMan real-time PCR of extracted DNA, and subsequent identification of alleles associated with investigated polymorphic SNP by means of allele-specific 5' nuclease assay, using the pre-developed assay and Custom TaqMan® SNP Genotyping reagents for allelic discrimination by TaqMan real-time PCR on AbiPrism 7900HT Sequence Detection System (Applied Biosystems, Foster City, CA). The above will involve following genes and polymorphisms: CYP3A5

#### Amendment 6Page 8 of 18

IRB # 38115 Version: December 28, 2018

gene: 6986 A>G (alleles \*1 and \*3) and ABCB1 (MDR1) exon26 (3435C>T) and exon21 (2677G>T/A).

# 7.0 Risks and Discomforts

The following adverse reactions have been described with everolimus: Leukopenia, the development of increased cholesterol and hyperlipidemia (high blood fats) levels, thrombocytopenia, anemia and a predisposition for viral, bacterial and fungal infections due to the immunosuppressant effect of everolimus. Hemolytic uremic syndrome, surgical wound complications, venous thromboembolism, acne and hypertriglyceridemia have also been described. Additional common side effects observed in transplant patients taking everolimus include hypertension, gastrointestinal disorders and edema. In two adult kidney transplant studies, less than 5% of the patients exhibited the combination of low testosterone and sexual dysfunction as an adverse event. However, the clinical implications of this are not clear.

Side effects of calcineurin inhibitors such as tacrolimus and cyclosporine are well described and include nephrotoxicity, neurotoxicity, hyperkalemia, and hypomagnesemia. Cyclosporine also causes hypertension, hepatotoxicity, hirsutism, hypertension, hyperlipidemia, gingival hyperplasia and sinus congestion. Unlike cyclosporine, Tacrolimus causes alopecia, may have a diabetogenic effect and causes less disturbances in lipid metabolism. Allergic reactions can occur with tacrolimus depending on the formulation, especially if castor oil is used.

#### Side effects of lothalamate clearance test:

Rare allergic reactions to iothalamate in subjects known to be allergic to iodine. Can range from urticaria to anaphylactic shock. Other adverse effects of iothalamate include arrythmias, bradycardia, generalized vasodilation, extravasation of iothalamate during injection, seizures, and weakness of extremities. Abnormal sensation or muscle spasm in the injection site has been reported but in patients being infused with five to thirteen times the amount planned in this study and at a faster infusion rate.

Mycophenolic acid has bone marrow suppression as the main side effect and rarely may have neurotoxicity associated with it. It is also an enteric coated formulation and hence should have less of the GI side effects such as nausea, vomiting and diarrhea, than mycophenolic mofetil which is a similar drug.

Given that arm A will consist of the patients on everolimus and mycophenolic acid, with complete withdrawal of calcineurin inhibitor, there will be a risk of bone marrow suppression and leucopenia, which will be dosage dependent.

Both calcineurin inhibitors and mycophenolic acid increase the patient risk for cancer, especially post transplant lymphoproliferative disease. Everolimus is thought to have an antiproliferative effect and may reduce the risk for the development of cancer.

All patients will be monitored closely for any of the above side effects. Other than the scheduled study clinic visits and testing, allpatients will be followed as per the Penn State Division of Transplantation follow up guidelines. For the first 24 months post liver transplant all our patients undergo the following routine lab collection procedure, the frequency of which may be adjusted based on patient clinical status and need:

Routine/standard of care laboratory tests from post op month 1 through post op month 24 include: :

✓ 1st 5 months postop: 2x/week labs as follows: Sodium, Potassium, Chloride, Bicarbonate level, BUN, Creatinine, Magnesium, Calcium, Phosphorus, CBC, PT, INR, PTT, Liver Function Tests (Total & Direct Bilirubin, AST, ALT, Alkaline Phosphatase & Gamma Glutamyl Transferase), Glucose & Immunosuppressive agent trough levels. Lipid Panel to be performed once a week.

PRAMS00038115 Approval: 1/7/2020

IRB # 38115

# Protocol

Version: December 28, 2018

- ✓ Month 6 to 12 inclusive: q weekly labs: Sodium, Potassium, Chloride, Bicarbonate level, BUN, Creatinine, Magnesium, Calcium, Phosphorus, CBC, PT, INR, PTT, Liver Function Tests (Total & Direct Bilirubin, AST, ALT, Alkaline Phosphatase & Gamma Glutamyl Transferase), Glucose, Immunosuppressive agent trough levels and Lipid Panel.
- ✓ After month 12: q2weekly labs: Sodium, Potassium, Chloride, Bicarbonate level, BUN, Creatinine, Magnesium, Calcium, Phosphorus, CBC, PT, INR, PTT, Liver Function Tests (Total & Direct Bilirubin, AST, ALT, Alkaline Phosphatase & Gamma Glutamyl Transferase), Glucose, Immunosuppressive agent trough levels and Lipid Panel.

Any abnormal laboratory values routinely result in a complete evaluation of the patient which may also include radiologic studies and a liver biopsy. Dose adjustments &/or discontinuation of medications may be required.

#### Years 2 & 3 Post Liver Transplant:

At 24 months post transplant patient's will have their final study visit and will be followed by the Divisions of Tranplant and Hepatology per standard of care. Labwork includes: Sodium, Potassium, Chloride, Bicarbonate level, BUN, Creatinine, Magnesium, Calcium, Phosphorus, CBC, PT, INR, PTT, Liver Function Tests (Total & Direct Bilirubin, AST, ALT, Alkaline Phosphatase & Gamma Glutamyl Transferase), serum Glucose, Immunosuppressive agent trough levels and Lipid Panel.

#### Clinic Visits: Year 1:

1x/week x 1 month Every 2 weeks x 1 month If stable: clinic visit x 1 at 1, 3, 6 & 9 months

Any persistent elevation in liver function tests (on consecutive testing within 1 week) or clinical issues: patient is brought to clinic regardless of scheduled clinic visits.

#### Years 2 & 3 inclusive:

Clinic every 3 months, unless elevation in liver function tests (persistent on 2 consecutive tests over a 1 week period) or if medication change or if clinical symptoms/complaints. If the latter occurs, patients should be seen in clinic during that week.

All patients undergo a full history and physical examination during their clinic visit associated with a complete review of their laboratory results and their current medications.

In this study, patients will be monitored for the development of medication side effects:

Everolimus & Mycophenolic Acid:

For patients who are unable to tolerate the protocol-specified dosing schedule of everolimus, dose adjustments will be made according to the following guidelines:

The everolimus dose will be decreased by at least 0.25 mg b.i.d if a dose reduction is necessary. If a temporary reduction in everolimus level is needed, the everolimus trough blood level will be maintained no lower than 3 ng/mL. Everolimus will be discontinued if a trough level  $\geq$  3 ng/mL cannot be maintained due to toxicity. Severe and unremitting changes/side effects may also lead to everolimus discontinuation.

IRB # 38115

# Protocol

If everolimus is interrupted for safety reasons for longer than 21 consecutive days, or for more than 2 episodes of 7 days or longer, discontinuation of study medication will be maintained and the patient will be removed from the study.

During the course of the trial everolimus will be administered on a b.i.d. regimen. Everolimus will not be provided to patients after they have discontinued the study.

If reduction of everolimus is necessary for the patient to remain in target trough range, everolimus dosing will be reduced by 0.25 mg intervals.

In cases of hyperlipidemia, lipid lowering therapy will be optimized before dosage reduction of study medication is considered. Patients will be managed with HMG Co-A reductase inhibitors (e.g., fluvastatin). Lovastatin or simvastatin will not be utilized. The starting dose of HMG Co-A reductase inhibitors will be equivalent to 20 mg pravastatin or 20 mg fluvastatin, and may be increased to target with the aim of maintaining a LDL level of < 130 mg/dL. Patients will be monitored for the development of rhabdomyolysis or other adverse events.

Both everolimus and mycophenolic acid have a bone marrow suppressant effect and predispose patients to neutropenia. Patients who develop neutropenia with an absolute neutrophil count (ANC) <1000 will be initially treated with administration of neupogen (filgrastim) at a dose of 5mcg/kg/day subcutaneously prior to dose reduction of immunosuppressant agents. If there is no response to neupogen therapy after 3 consecutive treatment days, dose reduction of mycophenolic acid, a dose reduction in everolimus should be undertaken as outlined below.

#### Guidelines for everolimus dose reduction/interruption:

	Platelet count (/mm3)	Hemoglobin (g/dL)	ANC count (K/UI)	Cholesterol (mmol/L)	Triglycerides (mmol/L)
Dose reduction	≤ 75,000	≤ 8	≤ 1000	≥ 8	≥ 6.5
Interruption	≤ 50,000	≤ 6	≤ 500	≥9	≥ 8.5

All patients will be carefully assessed for any of the side effects or adverse reactions related to everolimus through a detailed history and physical examination during clinic visits as listed above and through a thorough and complete examination of their routine and study laboratory values.

A foley catheter placement is required during iothalomate testing to accurately measure urine output collection. Risks of foley catheter placement include: pain, hematuria, injury to urethra, urinary retention following removal of foley, urinary tract infection and bladder spasms.

Patients will be withdrawn from the study in the event of a serious life threatening adverse event.

# 8.0 Benefits

Everolimus has a profile of anti-lymphoproliferative and anti-angiogenic effects in addition to its immunosuppressant effects and lacks nephrotoxicity. The main benefit of this study relates to renal sparing in patients in arm A, who will be converted from a calcineurin based immunosuppressive protocol to everolimus in combination with mycophenolic acid between 90 days-120 days post operatively. Thus the main benefit which is being evaluated in this study will be improvement and stability in renal function compared to patients on long term calcineurin inhibitors, which in the long run is believed to result in better long term survival outcomes.

# 9.0 Reporting of Adverse Events and Unanticipated Problems Involving Risks to Participants or Others

Amendment 6Page 11 of 18

IRB # 38115 Version: December 28, 2018

All adverse events (AE) will be documented on study specific case report forms and entered into a computer based log. All deaths on study, not related to progression of underlying disease, will be reported to the IRB and study sponsor immediately. All unanticipated AEs related or possibly related to the study will be reported by the PI to the IRB according to HSPO policies and procedures.

# **10.0 Study Withdrawal/Discontinuation:**

This is a small pilot study (12 randomized patients in each of two groups) and in view of the small patient cohort. Stopping rules for this study will therefore be based on patient safety.

#### **Monitoring Process:**

Primary monitoring of the study will be performed by the study team, who will review accrual, adverse events, and dose limiting toxicities on a real-time basis. Cumulative adverse events and study toxicities will be reviewed weekly. The study team will make decisions regarding dose escalation, cessation of accrual, and whether stopping rules have been reached. A Data Safety Monitoring Board (DSMB) has been created and its members are listed in the study protocol at the end of Section 13. The DSMB will review the study progress reports provided to the DSMB by the study team and a statistician. A DSMB report will be generated by the DSMB and forwarded to the IRB and the PI. A copy of any interim DSMB reports will be included with continuing review reports submitted by the PI for IRB review.

If stopping rules have been reached, this will be communicated to the IRB immediately.

Serious adverse events that would qualify for patient removal from study would include:

- Refractory leucopenia ≤ 500 unresponsive to drug dose reduction/interruption or stimulation by Neupogen (filgrastim).
- Persistant thrombocytopenia at <50,000/mm3, unresponsive to study medication dose reduction/interruption.
- Refractory hyperlipidemia (Cholesterol ≥ 9 mmol/L or Triglycerides ≥ 8.5 mmol/L ) unresponsive to treatment (as outlined in section 7 of the protocol) and to study medication dose reduction/interruption.
- Refractory anemia (Hemoglobin ≤ 6 g/dL) not related to surgical bleeding, and unresponsive to blood transfusion and to study medication dose reduction/interruption.
- Development of hemolytic uremic syndrome
- Development of any thrombotic events such as liver graft hepatic arterial or portal/hepatic venous thrombosis, or thrombotic microangiopathy or thrombotic thrombocytopenic purpura, or radiologically documented pulmonary embolism.
- Refractory seizures or neurologic side effects unresponsive to treatment or reduction/interruption of study medication.
- Life threatening infectious complications.

#### Reasons for discontinuation of the study drug everolimus will include:

• AE(s)

- · Abnormal laboratory value(s)
- · Abnormal test procedure result(s)
- · Unsatisfactory therapeutic effect
- · Significant protocol deviation
- · Withdrawal of consent
- · Lost to follow-up
- Death

Amendment 6Page 12 of 18

IRB # 38115 Version: December 28, 2018

#### · Graft Loss/Re-transplant

#### Premature Patient withdrawal:

Patients may voluntarily withdraw from the study or be dropped from it at the discretion of the investigator at any time. Patients will be withdrawn from the study if any of the following occur:

- Withdrawal of consent
- Lost-to follow-up
- Graft loss/re-transplant
- Death
- Serious life threatening adverse event.

If such withdrawal occurs, or if the patient fails to return for visits, the primary reason for a patient's premature withdrawal from the study will be recorded.

For patients who are lost to follow-up, "due diligence" will be shown by documenting in the patient record steps taken to contact the patient, e.g. dates of telephone calls, registered letters, etc.

Patients who are prematurely withdrawn from study medication or from the study after randomization will not be replaced. Patients who withdraw or screen fail prior to randomization will be replaced.

Patients who prematurely discontinue everolimus will be followed for any SAE occurring within 30 days following the last dose of everolimus. These SAEs will be reported on the SAE form.

Patients who become pregnant while taking everolimus or are taking a prohibited immunosuppressive medication not allowed by the protocol will be discontinued from the investigational drug and from the study.

If the everolimus trough level ≥ 3 ng/mL cannot be maintained, patients will be discontinued from the study.

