#### Protocol

Version: December 28, 2018

Visit number	1 Screening*	2 Baseline*	3	4	5
Time of Visit	90days-120 days post transplant	90days- 120 days post transplan t	Month 6 +/- 2 weeks***	Month 12 +/- 2 weeks ***	Month 24 +/- 2 weeks ***
Inclusion/Exclusion criteria	Х	Х			
Informed consent	Х				
Physical examination(medical history and vital signs	Х	Х	х	х	Х
Clinical assessment	Х	Х	Х	Х	Х
Quality of Life Questionnaires (FACT-Hep; EQ-5D)	Х	Х	Х	Х	Х
Dispense study medication		Х			
Return study medication					х
Laboratory test (blood & urine collection)	Х	Х	Х	Х	Х
Adverse events		Х	Х	Х	х
Blood test-HIV, hepatitis viruses, CMV and genotyping	Х				
Pregnancy Test	Х				
Concomitant Medications (Standard of Care) **					
Valcyte	Х	Х			
Bactrim(PCP prophylaxis)	Х	Х	Х	Х	
Mycophenolic acid (Myfortic)	Х	Х	Х	Х	Х

\* If the patient meets all inclusion criteria at the Screening Visit, the Screening and Baseline visits may occur on the same day and will occur between 90 days and 120 days post transplant.

\*\*All patients receive CMV prophylaxis with Valcyte in the 1st 4 postoperative months as part of standard care. Bactrim prophylaxis against Pneumocystis carinii is administered for the first year post transplant as part of standard care. Steroids are discontinued at 3 months post-transplant while Myfortic is continued as part of the maintenance immunosuppressive protocol.

\*\*\*Visit window for follow up visits at months 6, 12 and 24 is plus or minus 2 weeks

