# **11.0** Statistical Analysis of the Study

The primary endpoint of the trial is a renal function as assessed by 24 hour creatinine clearance.

We will compare creatinine clearance between the two arms of the study using a t-test. We expect that due to randomization there will be no differences in baseline characteristics of the two groups, so no multivariate analyses are planned. However, if we find significant difference between the two groups in such variables as demographics or disease characteristics, we will control for these variables in a linear regression analysis. In addition, we will also explore the use of nonparametric tests (i.e. Mann-Whitney U test for renal function) because of the relatively small sample size.

Secondary endpoints will also be tested using univariate statistical tests. The presence of acute rejection will be compared between study arms using chi-square tests. We will also fit nonparametric survival models to the time to acute rejection to determine whether rejection occurs earlier or later between study arms. Patient and graft survival will be modeled using Kaplan-Meier curves, with comparisons made between arms using the log rank test. To study the effect of donor and recipient genotype testing on postoperative renal function we will study the interaction between treatment arm and presence of CYP3A and P-gp SNPs on creatinine clearance. This will be done using a one-way analysis of variance with main effects for treatment and SNPs, and interaction terms between treatment and the SNPs.

Safety endpoints are all binary indicators (discontinuation, change of therapy, hyperlipidemia, etc.). All of these safety endpoints will be compared between treatment arms using chi-square tests.

Amendment 6Page 13 of 18

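### Stated safety follow-up after stopping treatment is tied to everolimus, so harms are observed for different lengths of time in the two arms

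*Combined protocol and SAP*

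**What the plan says.** All places are in the combined protocol and SAP.

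- **Section 10.0, Premature Patient withdrawal.** "Patients who prematurely discontinue everolimus will be followed for any SAE occurring within 30 days following the last dose of everolimus". The same subsection adds: "If the everolimus trough level ≥ 3 ng/mL cannot be maintained, patients will be discontinued from the study". A general list, not limited to one arm, opens with "Patients will be withdrawn from the study if any of the following occur" and covers consent withdrawal, loss to follow-up, graft loss, death and life-threatening adverse events.
- **Section 10.0, list of reasons to stop the drug.** It is headed "Reasons for discontinuation of the study drug everolimus will include". There is no matching list for the calcineurin inhibitor (CNI). It includes adverse events, abnormal laboratory values and unsatisfactory effect, which are not in themselves grounds for leaving the study in the general list.
- **Section 7.0.** If everolimus is interrupted for safety for more than 21 consecutive days, or for more than two episodes of 7 days or longer, "discontinuation of study medication will be maintained and the patient will be removed from the study".
- **Section 13.0.** The study team follows participants for adverse events during study treatment.
- **Section 6.0, evaluation schedule.** Adverse events are marked at Baseline and Months 6, 12 and 24, with no split by arm or by drug status. Section 7.0 sets the end: "At 24 months post transplant patient's will have their final study visit".
- **Section 11.0.** Safety endpoints are binary indicators, and "All of these safety endpoints will be compared between treatment arms using chi-square tests". Acute rejection is also compared by chi-square, alongside a time-to-rejection analysis. Patient and graft survival use Kaplan-Meier curves and the log rank test.

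**The concern.** The trial compares two strategies, conversion and continuation. Harms after a failed conversion are consequences of the conversion strategy. Yet every stated rule that shortens safety observation because assigned treatment stopped refers to everolimus, and so can act only in Arm A. The patients affected are those who stopped everolimus, often for toxicity or lack of effect.

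A chi-square test on the proportion with an event treats each patient as observed for the same time. If some Arm A patients are observed for a few months and Arm B patients for about 20, equal true risk shows up as a lower proportion in Arm A. With 12 patients per arm, one or two uncollected events visibly change the reported percentages.

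**Working it through.** **1. Which rules reach which patients.**

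| Situation | Stated safety follow-up |
|---|---|
| Arm A, stops everolimus, not removed from study | 30 days for SAEs (Section 10.0), but the Section 6.0 schedule still marks adverse events to Month 24: ambiguous |
| Arm A, removed for long interruption or unmaintained trough | 30 days for SAEs; study visits end; nothing provides for later harms |
| Arm B, CNI stopped or changed, still on study | Adverse events at Months 6, 12 and 24; no drug-anchored limit |
| Arm B, withdrawn under the general criteria | No post-withdrawal window stated |

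Section 7.0 treats a trough that cannot be maintained because of toxicity as a reason to stop everolimus. Section 10.0 treats an unmaintained trough as a reason to leave the study. The two must be reconciled before one can say who stays under observation.

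**2. Planned observation time.** Randomization is at day 90 to 120 after transplant, and the final visit is at 24 months, taken as day 730. Follow-up F is therefore 730 − 120 = 610 to 730 − 90 = 640 days.

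**3. Observation lost by one stopper, if the 30-day window is the limit.** For stopping T days after randomization, the unobserved share is 1 − (T + 30)/F.

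| T (days) | Observed (days) | Unobserved share, F = 610 to 640 |
|---|---|---|
| 30 | 60 | 90–91% |
| 90 | 120 | 80–81% |
| 180 | 210 | 66–67% |
| 365 | 395 | 35–38% |

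**4. Averaged over stopping times.** With a constant event rate, the unobserved time share equals the share of expected post-randomization SAEs outside the window.

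- Stopping uniform over the first 183 days (mean 91.5): 1 − 121.5/610 = 0.80; 1 − 121.5/640 = 0.81.
- Stopping uniform over all of follow-up: (F − 30)²/(2F²) = 0.45 for both values of F.

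**5. Share of all expected Arm A SAEs.** The documents give no discontinuation rate, so the number of stoppers is an assumption.

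| Stoppers of 12 | Early stopping | Stopping over all follow-up |
|---|---|---|
| 2 | 2/12 × 0.80 = 13% | 2/12 × 0.45 = 7.5% |
| 3 | 3/12 × 0.80 = 20% | 3/12 × 0.45 = 11% |

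**6. Effect on the proportion with at least one SAE.** Assume the same true risk p in both arms to Month 24, F = 625, and 3 of 12 Arm A patients stopping at day 90. The hazard is −ln(1 − p)/625, and a stopper is observed for 120 days. For p = 50%, a stopper's observed risk is 1 − 0.5^(120/625) = 12.5%. Arm A then shows (9 × 50% + 3 × 12.5%)/12 = 40.6%, against 50% in a fully followed Arm B. For p = 30% the Arm A figure is 24.2%, and for p = 70% it is 57.7%.

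The plan states no event rate or power for safety, so it has no figure of its own to reproduce here.

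**The case against.** Four points on the other side have force.

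- **A reader might infer that SAE collection ends at day 30 for every stopper.** The text does not say so. Section 10.0 distinguishes withdrawal from medication from withdrawal from the study, and the adverse event row in Section 6.0 is not conditional on drug status. For patients off drug but on study, what stands is an ambiguity. For those removed from the study it is not ambiguous: their visits end and no later collection is provided for.
- **A reader might infer that Arm B loses nothing.** Arm B patients can leave under the general criteria, and several of the serious events in Section 10.0 that lead to removal are not specific to everolimus. A withdrawn Arm B patient has no stated SAE window at all, so in that subgroup the asymmetry runs the other way. What Arm B lacks is a loss triggered by stopping its own drug.
- **Rejection, graft loss and death have their own analyses.** Time to rejection and survival are analysed with methods that allow for unequal follow-up, so it would be wrong to call these outcomes simply hidden. Two things remain: the yes/no rejection test has no such allowance, and removal after a failed conversion is unlikely to be independent of later risk, so the censoring is informative.
- **The named safety endpoints are less exposed.** Section 11.0 gives discontinuation, change of therapy and hyperlipidemia as examples and does not name SAEs. Discontinuation and the change of therapy that goes with it occur at the stop, and count against Arm A. Routine laboratory panels include lipids to Month 24. The list is open-ended, however, and any indicator arising after removal is affected.

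Chance also dominates at this size. In step 6 the shift is 9.4 points, or about 1.1 patients of 12, while the standard error of the difference is √(2 × 0.25/12), about 20 points. That limits the inference in any case. It is no reason to accept a shift whose direction is predictable.

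**Conclusion.** The concern stands as a difference between arms in stated safety follow-up, partly explicit and partly ambiguous. Followed as written, the rules give shorter harm observation in Arm A among the patients who tolerated conversion worst, and the chi-square comparisons do not allow for it. The tendency is to favour conversion whenever Arm A patients stop early and risk continues.

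The size is conditional. Under a constant event rate and early stopping, about 80% of a stopper's expected SAEs since randomization lie outside the window, which is about 20% of expected Arm A SAEs with 3 stoppers. If stopping is spread over all of follow-up, the figures are 45% and 11%. These assume that the 30-day window is the operative limit. The 80% could be misread as a share of events after stopping. It refers to all events since randomization; under the same assumptions the share of post-stopping events is about 94%. The documents do not support a claim that a particular number of events will be missed.

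**What to change.** Reconcile the Section 6.0 schedule, the interruption and trough text in Section 7.0, the withdrawal text in Section 10.0 and the monitoring text in Section 13.0, as follows:

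1. Collect adverse events, SAEs, rejection, graft loss and death from randomization to Month 24 in both arms, whether or not assigned treatment continues, subject to consent.
2. Separate stopping the drug from leaving data collection. This concerns data only and alters no treatment-stopping rule.
3. In Section 11.0, compare harms by randomized arm. Where follow-up is incomplete, use time to first event or exposure-adjusted rates, and report the observation time in each arm.
4. Keep the 30-day post-dose window as a supplementary on-treatment listing.

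The cost is protocol wording, some extra forms, and abstraction of data from routine visits for patients who stop treatment. Section 7.0 already describes standard-of-care laboratory and clinic follow-up at the centre over this period. Amending the 30-day sentence alone would not be enough, because the removal rules would still end study visits.

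### Everolimus-specific rules take Arm A patients out of the study, not only off the drug, and the plan secures neither the later primary endpoint nor an analysis rule for them

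*Combined protocol and SAP*

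**What the plan says.** Three rules tied to everolimus end study participation.

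- Trough (Section 10.0, Premature Patient withdrawal): "If the everolimus trough level ≥ 3 ng/mL cannot be maintained, patients will be discontinued from the study."
- Interruption (Section 7.0): "If everolimus is interrupted for safety reasons for longer than 21 consecutive days, or for more than 2 episodes of 7 days or longer", then "discontinuation of study medication will be maintained and the patient will be removed from the study."
- Pregnancy (Section 10.0): "Patients who become pregnant while taking everolimus or are taking a prohibited immunosuppressive medication not allowed by the protocol will be discontinued"; the sentence goes on to name both the investigational drug and the study.

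Other removal rules carry no explicit arm restriction. Section 10.0 covers graft loss and investigator discretion: "Patients may voluntarily withdraw from the study or be dropped from it at the discretion of the investigator at any time." Section 7.0 covers severe events: "Patients will be withdrawn from the study in the event of a serious life threatening adverse event."

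On follow-up after everolimus stops, Section 10.0 says: "Patients who prematurely discontinue everolimus will be followed for any SAE occurring within 30 days following the last dose of everolimus." It also has the primary reason for withdrawal recorded and does not replace patients lost after randomisation.

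Section 11.0 names 24-hour creatinine clearance as the primary endpoint, to be compared by t-test. Survival is analysed by Kaplan-Meier and log-rank methods, and discontinuation is compared between arms by chi-square as a safety endpoint. It states no analysis set, no method for missing clearance and no censoring rule.

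On the same trough limit, Section 7.0 stops everolimus if a level of at least "3 ng/mL cannot be maintained due to toxicity".

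**The concern.** Section 2.0 frames the primary objective as the renal effect of putting a conversion strategy into practice. Patients who cannot hold an everolimus level, or cannot stay on the drug, are part of that strategy's result. The trough and interruption rules remove these patients, and they can act only in Arm A.

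If their later clearance is not collected, a t-test on whoever remains compares selected converters with an Arm B that was not selected in the same way. That answers a different question and loses the protection of randomisation. The same gap reaches the survival analyses, where nothing says whether removal censors a patient or whether a death after graft loss counts. It also reaches the cost-effectiveness ratio, whose effectiveness measure is renal function. With 12 per arm and no replacement, each lost patient is a visible share of the arm.

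**Working it through.** **1. Which arm each rule can reach**

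| Rule | Place | Arm scope |
|---|---|---|
| Trough of 3 ng/mL not maintained | 10.0 | Arm A only |
| Everolimus interrupted too long or too often | 7.0 | Arm A only |
| Pregnancy while on everolimus | 10.0 | Arm A only; minor, since Section 4.0 requires contraception or non-child-bearing status |
| Prohibited immunosuppressant | 10.0 | Unclear: the text speaks of the investigational drug |
| Life-threatening event, graft loss, investigator discretion | 7.0, 10.0 | No restriction stated |
| Listed serious events | 10.0, Monitoring Process | No restriction stated; several depend on failed reduction or interruption of study medication |

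For Arm B, Section 6.0 gives calcineurin-inhibitor target levels but no removal rule attached to them.

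**2. What data remain after removal**

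The 24-hour urine collection is a scheduled study test (Section 6.0). The routine laboratory lists in Section 7.0 include serum creatinine but no 24-hour collection. Routine visits and laboratory work-up may show rejection, graft status and survival, but nothing says these will be used as outcomes for removed patients. Clearance measured before removal is kept.

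**3. The plan's own power, then the loss**

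Inputs from Section 11.0: 12 per arm, difference 9, SD 7.5 (alternative 16), two-sided 0.05, two-group t-test. These SDs are for eGFR and are used for creatinine clearance for lack of another figure. With k Arm A patients lost, the standard error is SD × √(1/(12−k) + 1/12), the noncentrality is 9 divided by it, and df = 22−k.

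- k = 0, SD 7.5: 7.5 × √(1/12 + 1/12) = 3.062; 9/3.062 = 2.939; power 80.2%. This reproduces the stated 80%. At SD 16, 51 per arm gives 80.3%, which also agrees.
- k = 3, SD 7.5: 7.5 × √(1/9 + 1/12) = 3.307; 9/3.307 = 2.721; power 73.3%.

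| Arm A patients lost | 0 | 1 | 2 | 3 |
|---|---|---|---|---|
| Power, SD 7.5 | 80.2% | 78.3% | 76.0% | 73.3% |
| Power, SD 16 | 26.1% | 25.1% | 24.0% | 22.8% |

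**4. A different question**

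Suppose the difference from Arm B is 9 in those who stay and g in those removed. The strategy difference is (9 × (12−k) + g × k)/12.

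- g = 0: 8.25, 7.5 and 6.75 for k = 1, 2 and 3, so leaving these patients out overstates it by 0.75, 1.5 and 2.25.
- g = 4.5: the overstatement is half that.
- g = 9: it is zero.

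**5. Selective removal with no true effect**

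Simulation, 400,000 trials per setting: 12 per arm, equal means, SD 7.5. A removal score has correlation r with clearance, the k lowest scorers in Arm A are left out, and a pooled t-test is applied.

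| k | r = 0 | r = 0.3 | r = 0.7 |
|---|---|---|---|
| 1 | bias 0, error 5.0% | 0.3 mL/min, 5.3% | 0.8 mL/min, 6.0% |
| 3 | bias 0, error 5.0% | 0.9 mL/min, 5.8% | 2.1 mL/min, 10.0% |

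The bias changes sign if patients with better renal function are the ones removed. Keeping all 12 as randomised gives bias 0 and error 5.0%.

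**6. The two trough rules**

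Section 7.0: the condition is failure to hold the level because of toxicity, and the consequence is that everolimus stops. Section 10.0: the condition is failure to hold the level for any reason, and the consequence is that the patient leaves the study. A patient whose level cannot be held for a reason other than toxicity meets the second rule and not the first.

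**The case against.** The strongest reply is that the plan is not silent. It records why patients withdraw, compares discontinuation between arms, treats stopping medication and leaving the study as separate things, and continues routine care for everyone. All of that stands. Unequal stopping would be visible, but none of it supplies the missing clearance or says who is analysed.

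A reader might infer that every everolimus stop ends follow-up. The documents do not support that. The visit schedule makes no exception for a patient who only stops the drug, and the 30-day sentence can be read as an SAE reporting window. The gap concerns patients removed from the study.

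A reader might also infer that all removal rules act only on Arm A. They do not. Although the only reduction and interruption table is for everolimus, Section 7.0 also provides for reducing mycophenolic acid, which both arms take.

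The magnitudes rest on assumptions. No removal rate is given, Arm B is assumed to lose nobody, and the stated triggers (drug level, blood counts, lipids) are not renal. The 10.0% error is the extreme setting, and the power loss is small beside the SD risk that Section 11.0 already admits. These points are right, so the figures illustrate and do not predict.

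On the trough, the two consequences are compatible: the drug can stop and the patient can leave. What differs is the toxicity condition and how far the consequence goes.

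Finally, Section 6.0 gives an end date of 1 October 2019, so some visits may be past recovery. That limits the remedy but does not remove the need for an analysis rule.

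**Conclusion.** The point holds and should be fixed. Followed as written, the trough and interruption rules, and to a minor degree the pregnancy rule, can remove the primary endpoint selectively from Arm A, while the stated objective needs the outcome of those same patients.

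With 1 to 3 of 12 Arm A patients lost, power at SD 7.5 falls by about 2 to 7 points. Bias runs from zero, if removal is unrelated to clearance, to about 2 mL/min in the most selective setting shown, against a planned difference of 9. This assumes that removed patients' data are left out at the analysed visit, that Arm B is complete, and that the eGFR SDs apply to creatinine clearance.

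A reader might infer that the plan is biased in favour of everolimus. The documents do not show this: they give neither a removal rate nor a link between removal and renal function, so size and direction are unknown.

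The two trough passages must be reconciled by the sponsor. No view is taken here on which clinical rule is right.

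**What to change.** Separate stopping study drug from ending follow-up. Suggested text for Section 10.0, with the interruption wording in Section 7.0 aligned to it:

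> Patients who stop study drug or meet a removal criterion remain in follow-up in both arms, unless they die, are lost to follow-up or withdraw consent for follow-up. 24-hour creatinine clearance (where feasible), rejection, graft status, SAEs and vital status are collected at the remaining Month 6, 12 and 24 visits.

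Suggested text for Section 11.0:

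> All randomised patients are analysed in their assigned arm. Stopping study drug or meeting a removal criterion is not a reason for censoring. Graft loss is an event for graft survival, and deaths after graft loss count for patient survival. The method for missing creatinine clearance is fixed before analysis. On-treatment results are supportive only.

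Where visits have already passed, take rejection, graft and vital status from routine follow-up, and report serum-creatinine-based renal function for removed patients as a sensitivity analysis. The sponsor should reconcile the trough wording of Sections 7.0 and 10.0 and state the arm scope of the prohibited-medication rule.

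Cost: one amendment, and at most three already scheduled 24-hour urine collections for each of a few patients. Those collections are outside routine care, so they are a real burden on patients who have left treatment. Clearance at visits already missed cannot be recovered.
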